right insula. Another group will receive TI-NDBS over the nucleus accumbens. Another group will receive TI-NDBS to the anterior cingulate cortex. We will not target these brain areas in any particular order. Prior to stimulation, subjects will be administered a questionnaire to assess their physical experiences and sensations using a 5-point Likert-scale. Subjects will also be given the Nicotine Dependence Syndrome Scale to assess baseline Nicotine Dependence. In addition, we will measure total real-time ad lib nicotine vapor inhalation during a 60 minute stimulation session. At the start of the stimulation, the current will increase slowly at a constant rate for 30 seconds until it reaches the appropriate intensity. At the end of the stimulation, the current will decrease slowly for 30 seconds until it reaches zero. Every ten minutes, we will ask subjects to self-report their level of craving on a Likert scale of 1-10. We will identify whether TI-NDBS to the insula or nucleus accumbens or cingulate is more effective stimulation at decreasing cravings. In the second stage of Phase 3, we will take the two most promising of the three brain regions and repeat the procedure of stage 1, but with a larger sample size. The third group will receive sham stimulation as a control. In both stages, immediately after stimulation, subjects will complete the stimulation experience scale and then again 30 minutes later. We will then follow up with subjects every day, up to three times per day, for a period of 1 week afterward using Ecological Momentary Assessment (EMA) via a smartphone app (LifeData) to monitor cigarette and/or vaping use and craving. The questions that will be used in the app are in a script attached (see EMA follow up questions). In Phases 1, 2, and 4 subjects are paid \$25/hr. In Phase 3, subjects are paid \$40/hr. In addition, in Phases 3 and 4, subjects are paid \$5/day for providing ecological momentary assessment data outside of the lab sessions, and \$10 bonus for completing 7 consecutive days of ecological momentary assessment (EMA). Payment will be made at the end of each day's lab session in cash, and for phase 3, by check after the EMA period ends.

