#### **Safety and Monitoring:**

- 1. Comfort:** Subjects will be asked to rate (1-5 scale) severity, location and quality (self described) of any discomfort using the attached stimulation experience scale immediately prior to the stimulation, immediately after each 10 minute stimulation block, and at 10 minutes after the stimulation session. If any discomfort persists at 10 minutes after stimulation, treatment and ongoing assessment will be arranged as needed by the study physician.
- 2. Cognitive Effects:** Baseline memory, attention and verbal reasoning will be assessed using the Digits span test from the WASI, which assesses short-term memory and attention. This will be repeated 10 minutes after the stimulation. Subjects will also be asked open ended questions about any changes in their thinking or cognitive status.
- 3. Psychiatric Effects:** Emotional, motivational and behavioral symptoms will be assessed using the PANAS (Positive and Negative Affect Scale) before stimulation and immediately following stimulation.
- 4. COVID-19 safety:** Subject and experimenter, both wearing masks, enter the testing room. Experimenter places electrodes on subject's head and adjusts them. Experimenter gives the subject an e-cigarette mouthpiece and an exhaust device to exhale into (which has a carbon and HEPA filter to filter the subject's exhaled breath and nicotine vapor), with instructions for the subject to remove their facemask after the experimenter has left the room, inhale from the e-cigarette per protocol, and exhale into the exhaust device. Experimenter leaves the room, after which subject removes their own facemask. Subject proceeds to do the experiment and puts their facemask back on before the experimenter again enters the room.

**Phase 4. Relative effectiveness of stimulation.** In phase 4, we will compare TI-NDBS vs.

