conventional transcranial direct current stimulation for smoking reduction. To test this, we will recruit another group of subjects who are heavy smokers into three groups, then ask them to abstain from smoking. Prior to stimulation, subjects will be given the NDSS to determine baseline nicotine dependence. The first group will receive standard transcranial direct current anodal stimulation of the right DLPFC and cathodal stimulation of the left DLPFC (F3 and F4 in the 10/20 system). The second group will receive TI-NDBS to either the nucleus accumbens or anterior insula or anterior cingulate, depending on which is found to be more effective in Phase 3. The third condition will be sham. The strength of the stimulation and duration will be the same as in previous phases. Prior to stimulation, subjects will be administered a questionnaire to assess their physical experiences and sensations using a 5-point Likert-Scale. Immediately after stimulation, subjects will complete the stimulation experience scale, then complete the scale again 30 minutes later. In addition, we will assess craving levels every 10 minutes during the stimulation period. We will repeat this for five consecutive days. We will then follow up with subjects every day, up to three times per day, for 1 week after starting the tDCS, using EMA via a free smartphone app (ilumivu.com) to monitor cigarette use and craving. The questions that will be used in the app are in a script attached (see EMA follow up questions). We will compare the sham vs. tDCS vs. TI-NDBS groups to identify differences in craving and relapse. We expect to find that TI-NDBS leads to reduced craving and drug use relative to sham or tDCS. The procedure in this phase will not add anything new, except testing subjects with tDCS in addition to TI-NDBS and sham.

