## Safety – TI-NDBS device

The TI-NDBS device has the following safety features, designed to prevent malfunction and, if a malfunction were to occur, automatically reduce the electrical current to prevent injury to the patient:

- 1) **Intrinsic limits:** It has a 9 volt power supply, which limits the electrical stimulation power that can be delivered.
- 2) **Safety monitoring circuit:** It has a built in voltage monitor to detect malfunctions and take corrective action. The device is designed to deliver a fixed amount of current, up to 2 mA per channel. The voltage is constantly adjusted to compensate for the electrical resistance of the

head and maintain the desired electrical current. If the resistance increases such that the voltage reaches the maximum possible device voltage (e.g. due to a poor connection with the scalp), then the device will signal an error via an LED light and lower the set point current to avoid excessive voltage. In plain language, the device has a built-in monitor that will immediately detect malfunction and reduce the current.

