### **TI device**

The TI device was custom-built by the machine shop in the department of Psychological and Brain Sciences based off of schematics that [name] (PI) and [name] (Ph.D., electrical engineer) devised based on the work of Grossman et al. 2017 (for device images and circuitboard diagram see the Notes & Attachments). The TI device contains a mechanism that constantly monitors the amount of current administered via the electrodes. The current study design is single-blind such that the experimenter will become aware of the amount of current administered to ensure the safety of experimental subjects. A prototype of the device is shown in Figure 2. The device has the following characteristics:

- The device is powered by standard 9-volt batteries that provides the energy to carry out the neurostimulation. The device may also be powered by a standard 9-volt power supply.
- There are two electrode pairs, with a total of 4 electrodes, that will connect from the device in Figure 2 to gel electrodes on the subject's head (as shown in Figure 1), typically of varying shapes approximately 2 cm x 2 cm. At 2 mA current, this will result in a maximum current density of  $0.0005 \text{ A/cm}^2$ . At 50Kohm scalp impedance, the total power dissipated by an electrode pair is  $I^2R = 200 \text{ mW}$ , which is comparable to the power emitted by a cell phone.
- Each electrode pair generates a sinewave alternating current, with no DC component. The frequency can be varied continuously from zero to over 5 Khz. We will not apply alternating current frequencies over 5Khz. Typically, the frequencies will be around 2 Khz.

- The frequency difference between the electrodes will be varied between 1-100 Hz.
- The current for each electrode pair can be controlled continuously from zero to 2 mA. Each of the two electrode pairs may have a different current level, which allows the focal point of stimulation in the brain to be steered without moving the electrodes.
- For safety, the device includes an onboard current monitor to measure the amount of current actually delivered. The device can be powered down if for any reason the amount of current exceeds the specified setting, or if the voltage required to deliver the current exceeds the device's capacity.

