- The device settings are controlled by a separate microcontroller, typically a Raspberry Pi zero, which communicates with the device via serial protocols, namely SPI and I2C. The raspberry pi is a fully functional computer that can be programmed to run timed stimulation protocols and control the neurostimulator.
- The four electrodes will be placed on the subject's scalp (Figure 1) at locations designated in the international 10/20 system, as used for EEG. The locations will be optimized by finite element modeling to target specific brain regions such as the dorsal anterior cingulate cortex (dACC), insular cortex, and nucleus accumbens.
- Should stimulation be terminated early for any reason, the same stimulation assessments will be conducted as if the session lasted the full 40 minutes including the EMA, stimulation experience scale, heart rate, blood pressure, psychiatric symptoms, nicotine craving, etc. The reason for termination will be recorded and an unanticipated event filed with the IRB. If the subject experiences an adverse reaction to the stimulation, this will be recorded and reported to the IRB and DSMB.

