**5.0 Outcome Characteristics and Endpoint Definitions:**

For Phase 1, we will determine if any participants report adverse reactions or any side effects from the TI-NDBS stimulation, using the Stimulation Experience Scale questionnaire. Some potential side effects include itching, unusual sensations, abnormal or unpleasant thoughts, or physical sensations. We will follow-up with participants after the stimulation session to determine if there were any side effects from TI-NDBS. For phase 2, we will measure the change in neural activity for each target area of the brain to be stimulated for TI-NDBS vs. no stimulation to determine if the activity is different for TI-NDBS stimulation, again using the Stimulation Experience Scale. For phase 3, we will determine whether TI-NDBS vs. sham leads to a difference in nicotine craving via self-report measures and corresponding reduced nicotine vapor inhalation in the MRI scanner. For phase 4, we will determine a difference in nicotine craving via self-report measures and corresponding reduced nicotine vapor inhalation in the MRI scanner between TI-NDBS and tDCS. We will also examine differences in neural activity measured by fMRI between TI-NDBS and tDCS.

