self report their level of craving on a Likert scale of 0-10. We will identify whether TI-NDBS over the insula or nucleus accumbens is more effective than sham stimulation. We will then follow up with subjects 1 week afterward, using ecological momentary assessment (EMA) via smartphone apps (ilumivu.com) to assess cigarette use and craving. We expect to find that TI- NDBS reduces craving and cigarette consumption relative to sham. **Analysis and predictions:** We predict that TI-NDBS will outperform tDCS at reducing smoking and cigarette craving, which in turn will outperform sham stimulation. We will sum the total inhaled nicotine vapor over the 60 minute session and perform pairwise t-tests to determine if total drug intake is lower with one of the stimulation groups vs. sham. Also, we will average the self reported craving levels across each subject during the 60 minute session, and we will perform pairwise tests to determine if stimulation lowers self reported craving. During the 7 days following the stimulation session, we will give subjects the ilumivu app on their smartphones (or a loaner phone if needed), and we will notify them daily to request a self report of their level of craving and cigarette use in the preceding 24 hours. We will average these measures for each subject and perform an omnibus ANOVA (time point by group), followed by post-hoc pairwise tests to determine whether the stimulation led to longer lasting effects relative to sham. We will perform post-hoc tests for each of the 7 days to identify any differences in the duration of stimulation effects. For a power analysis, we do not yet know how many subjects will be necessary to achieve statistical power in the second part of phase 3, because we do not yet know what the effect sizes are. Nevertheless we anticipate that 15 subjects per group will provide a solid estimate of the effect sizes of stimulation relative to sham, so that we can write a grant to scale up the number of subjects based on a power analysis.

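### Craving ratings in Phases 3 and 4 are not kept separate from staff who know the arm, so the comparison with sham is open to cueing of unknown size; timed self-entry would largely close the gap

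*Combined protocol and SAP*

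**What the plan says.** The only statement of the blinding level is in the TI device text of Section 3.0: "The current study design is single-blind such that the experimenter will become aware of the amount of current administered". The stated purpose is subject safety.

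Craving is an endpoint. For Phase 3, Section 5.0 says "we will determine whether TI-NDBS vs. sham leads to a difference in nicotine craving via self-report measures", and it names craving again for Phase 4. On collection, the Phase 3 text says "Every ten minutes, we will ask subjects to self-report their level of craving on a Likert scale of 1-10" and the Phase 4 text says "we will assess craving levels every 10 minutes during the stimulation period". On analysis, Section 6.0 says "we will average the self reported craving levels across each subject during the 60 minute session" and then applies pairwise tests. Phase 4 is to use the same tests, although the text calls their source Study 1, a label not used elsewhere.

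Side effects are collected in the same sessions. In Phase 3, discomfort is rated after each 10-minute block on the stimulation experience scale. In Phase 4 it is to be rated verbally. Both phases add open-ended questions about changes in thinking.

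On the experimenter's position, the COVID-19 item for Phase 3 says "Experimenter leaves the room, after which subject removes their own facemask". Before that, the same person fits the electrodes and gives instructions. Phase 4 has no matching text.

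On the equipment, the controller "can be programmed to run timed stimulation protocols and control the neurostimulator", and the device safety section says "the device has a built-in monitor that will immediately detect malfunction and reduce the current".

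**The concern.** In an active-versus-sham comparison, a person who knows the current knows the arm. Craving is a subjective rating, and how it is requested can affect the answer: tone, timing, a follow-up question, or what was said at set-up. The plan names no blinded rater, no self-entry of in-session ratings, no fixed prompt, no coded conditions and no check of blinding.

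Two results are at stake. One is the pairwise comparison of in-session craving, together with the side-effect comparison, which is collected in the same way. The other matters more given the stated purpose: Section 6.0 says that 15 subjects per group are meant to give an effect-size estimate on which a larger study will be powered. Any cueing shift enters that estimate in full. It cannot be removed in analysis, because knowledge of the arm coincides with the arm.

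**Working it through.** **Who can know what, by comparison**

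| Comparison | What reveals the arm | Source |
|---|---|---|
| Phase 3 pilot: three target sites, all active | Electrode placement; the current alone does not separate them | 3.0, Phase 3; 6.0 |
| Phase 3 second part: two sites vs sham | Current delivered (active vs sham); placement (site) | 3.0, TI device; 6.0 |
| Phase 4: TI-NDBS vs tDCS vs sham | Current delivered (active vs sham); placement, with tDCS at F3 and F4 and TI-NDBS using four electrodes in two pairs | 3.0, Phase 4 and New technology |

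**How exposed each outcome is**

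- In-session craving: subjective and requested by the team. A 60-minute session at 10-minute intervals gives 60/10 = 6 requests. Averaging six ratings reduces random error but leaves a consistent cueing shift untouched.
- Discomfort and cognitive questions: subjective; the Phase 4 discomfort rating is explicitly verbal.
- Vapor intake: measured by the device, so less exposed.
- Follow-up craving and cigarette use: entered in a smartphone app away from the laboratory, so less exposed.

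**Does the safety reason require the person collecting ratings to know the arm?** The documents describe software limits on current, an onboard monitor, and an LED error signal with a lowered set point. Someone may still need to watch the current. Nothing says that this person must also collect ratings.

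**Illustration of size.** The plan has no figure to reproduce beyond 3 × 15 = 45. It gives no SD, effect size, alpha or sidedness. Assumed: no true effect, two-sided alpha 0.05, and a cueing shift of b SD in the active arm.

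- n = 15 per group; df = 2 × 15 − 2 = 28; noncentrality = b × √(n/2) = b × √7.5 = 2.739b.
- Smallest observed difference reaching p < 0.05: t(0.975, 28) × √(2/15) = 2.048 × 0.365 = 0.75 SD.

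| Assumed shift b | Noncentrality | Rejection, either direction | Rejection favouring stimulation | At least one of two active arms favoured vs shared sham (simulated, 100,000 trials) |
|---|---|---|---|---|
| 0 | 0 | 5.0% | 2.5% | 4.5% |
| 0.2 | 0.55 | 8.3% | 7.6% | 13.0% |
| 0.3 | 0.82 | 12.5% | 12.2% | 19.8% |
| 0.4 | 1.10 | 18.5% | 18.4% | 29.0% |

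The last column assumes the same shift in both active arms and no multiplicity adjustment. Whatever the test result, the expected effect estimate moves by b. Set against the 0.75 SD threshold, 0.2 is 0.2/0.75 = 27% and 0.4 is 0.4/0.75 = 53%.

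**The case against.** A reader might infer that the experimenter who knows the current personally asks each subject about craving. The documents do not say so. They speak of the team asking and assessing, and in Phase 3 the experimenter is out of the room once set-up is done. Ratings there may already be self-entered; the text is silent. This stands, and it limits the point to a missing separation of roles. It does not dispose of it: leaving the room is an infection-control step, covers Phase 3 only, follows face-to-face set-up, and leaves the mode of collection open.

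A reader might also infer that the device needs no operator, so that the safety reason is empty. That goes too far. The controller can be programmed for timed runs, but unattended operation is not stated. The automatic response described is to voltage reaching its maximum. For current above the setting, the text says the device can be powered down, not that it does so by itself. The device is a custom-built prototype, and these features are described for TI-NDBS, not for tDCS hardware. Observing the current is a deliberate safety choice and should stay.

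Nor does knowledge of the current bias the choice of site in the pilot, where all three groups are active. Only electrode placement could do that, and coded programs would not hide it. Coded programs would likewise not make Phase 4 double-blind.

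Finally, in-session craving is one of several efficacy measures, and these phases claim no error rate or power. Both statements are correct.

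**Conclusion.** The point holds in a limited form. The study is declared single-blind, knowledge of the arm is available to the experimenter, and nothing in the plan keeps that knowledge away from the collection of in-session craving and side-effect ratings in Phases 3 and 4. The exposure is clearest in Phase 4, where discomfort is rated verbally and no text places the experimenter elsewhere.

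The size and direction of any cueing are unknown. The rejection rates of 8.3% to 18.5% follow mechanically from an assumed shift of 0.2 to 0.4 SD and an assumed two-sided alpha of 0.05. They are not estimates for this trial, nor a departure from an error rate that the plan states. The firmer consequence is that any shift passes undiminished into the effect size carried to the next study. Conclusions from measured vapor intake and app-entered follow-up are less affected.

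**What to change.** In Phases 3 and 4:

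1. Have subjects enter the 10-minute craving rating and the stimulation experience scale themselves, at a timed on-screen prompt with fixed wording and no experimenter involvement. This works the same way in every arm, whatever the electrode placement reveals. The craving scale must be reconciled first: it runs 1–10 in the Phase 3 description and 0–10 in the New technology text and Section 6.0.
2. Script the set-up instructions, since contact before stimulation would remain.
3. Leave current monitoring and the ability to intervene exactly as planned.

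Optionally, for TI-NDBS versus sham only, load the conditions as coded programs, if an existing team member who collects no outcomes can hold the code and keep access to the current log. The documents give no staffing list, so whether this is possible is for the sponsor to judge. It would mask neither the target site nor tDCS versus TI-NDBS.

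The cost is minor set-up work: a rating screen and a short script. No extra subjects, visits or procedures are needed.

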#### **4.0 Eligibility Criteria**

List the criteria:

Inclusion:

- between the ages of 18 and 50, must have at least a 6th grade education, ability to speak and read English for all phases.

Exclusion:

- if they are on psychotropic medications for ADHD, other mental illness or medication for cancer, epilepsy (i.e. individuals with any history of seizure disorder), migraines, or other neurological syndromes, or AIDs (which can cause cognitive deficits (Watkins & Treisman, 2015), history of head trauma, history of cognitive impairments, metal implants in the head or under the scalp, personal experiences consistent with symptoms of psychosis (i.e. hearing or seeing things that aren't there, being secretly controlled, or having special powers, seeing or hearing things that aren't really there).

• For phase 2, subjects will be excluded if they do not meet fMRI safety screening criteria (i.e. metal implants in their body, tattoo on head or neck, permanent jewelry, etc.) or if a participant uses an IUD for birth control they will be excluded unless the subject can document the model of the IUD and we can verify its safety for the MRI environment. Pregnancy should be self-reported, and a pregnant test will not be administered. Participants must weigh less than 440 lbs etc.

- History of holes bored into skull or known fissures in cranial bones
- Presence of pacemakers

• In phases three and four, subjects will be excluded if they do not smoke at least 3/4 pack of cigarettes per day on average and if subjects do not have access to a cell phone (or loaner cell

Indiana University, Bloomington, IN

phone) with internet access.

